### 6.2 Sample Size Considerations

No formal hypothesis testing will be performed, and the sample size is not based on statistical power considerations. The sample size was chosen based on experience with other studies conducted with compounds in early clinical development and on DRC recommendations. A population of about 6 to 10 subjects per dose is commonly tested in studies which aim to establish a tolerability range for a new compound or a new formulation and is used as a guide for a minimum cohort size for this study.

#### 6.3 Randomization

Approximately 200 women 18–45 years of age will be screened, and approximately 10-30 of those with PPD will be randomized within cohorts on Day 1 to receive ganaxolone or placebo in a 1:1 ratio with 1 block

PRS 005 T 17 F

of 4 for each cohort, while the rest of the blocks are of size 2. Treatment assignment will be determined by a randomization schedule prepared by PAREXEL. Randomization will not be stratified. Treatment assignments will be obtained by the investigator (or designee) via an Interactive Voice and/or Web Response System (IxRS). Subject numbers will be assigned sequentially as subjects consent to participate in the study. After being randomized a subject will be replaced only if she discontinues prior to receiving investigational product (IP). The replacement subject will receive the same IP assignment as the replaced subject.

### 6.4 Blinding

The unblinded pharmacist, unblinded medical monitor, independent reporting statistician/programmers, as well as the DRC are provided the treatment information prior to unblinding in order to ensure the optimal conduct of the study. In addition, any data transferred into PRA are processed by an unblinded database developer in order to ensure any potentially unblinding information is masked to the study team. All other study personnel remain blinded to treatment assignment until unblinding.

The unblinded statistician and programming team are external to PRA and have limited communication with the blinded statistician and programmers during the conduct of this study.

# 7.0 Study Variables and Covariates

### 7.1 Efficacy

### 7.1.1 HAMD17

The Hamilton Depression Rating Scale (HAMD) is a commonly-used semi-structured clinician-rated instrument which assesses the range of symptoms that are most frequently observed in subjects with major depression. All items are scored on an ordinal scale between 0 and 4 (8 items) or 0 and 2 (9 items) of increasing severity. A total score is derived by summing over all individual items. Improvement is indicated by negative change scores and this will be footnoted in the TFLs. The 17-item version of this scale (HAMD17) will be used in this trial and will be assessed at each in-person study visit . The Day 1 assessment before IP infusion will be the Baseline observation.

#### 7.1.2 HAMD6

Some items on the HAMD scale (such as weight) are not expected to have meaningful changes over the first 72 hours. The 6-item version of the HAMD, known as HAMD6, will be used as an additional measure of changes in symptoms of depression. The items on the HAMD6 scale are as follows: depressed mood, work and interests, general somatic symptoms (tiredness), anxiety, guilt feelings, and psychomotor retardation. The HAMD6 is considered to be responsive to more immediate changes in depression symptoms. Improvement is indicated by negative change scores and this will be footnoted in the TFLs.

### 7.1.3 Edinburgh Postnatal Depression Scale (EPDS)

The EPDS is a 10-question self-rated instrument for assessment of symptoms of PPD such as worry, sleep, mood and enjoyment, which are rated on a 4-point scale (0 to 3) of increasing severity. The EPDS total score is the sum of the scores of these 10 questions. Improvement is indicated by negative change scores and this will be footnoted in the TFLs.

Two questions assessing obsessive thoughts were added to this questionnaire ("How much of your time is occupied by obsessive thoughts over the past 24h?" and "How much distress do your obsessive thoughts

cause you?), but they are not counted towards the total EPDS score. These 2 questions are rated on a 5-point scale (0 to 4) of increasing severity.

The responses will be assessed at Screening, Day 1, +60h, Day 11, and Day 34 for the IV only cohorts and at each in-person visit for the IV to oral cohort. The Day 1 assessment before IP infusion will be the Baseline observation.

### 7.1.4 Spielberger Trait-State Anxiety Inventory, 6 item version

The Spielberger Trait-State Anxiety Inventory, six item version (STAI6), is a short questionnaire evaluating anxiety state. The STAI6 has 6 questions: 1) "I feel calm", 2) "I am tense", 3) "I feel upset", 4) "I am relaxed", 5) "I feel content", and 6) "I am worried". Each of these questions are rated as a) "not at all" b) "somewhat", c) "moderately", and d) "very much." For questions 2, 3, and 6, the scoring is a=1, b=2, c=3, and d=4. For the other 3 questions, the scoring is a=4, b=3, c=2, and d=1. The STAI6 score is the result of first totaling the 6 individual item scores, and then prorating it by a multiplication factor of 20/6 to acquire a range of 20 to 80, inclusive (Marteau 1992). Improvement is indicated by negative change scores and this will be footnoted in the TFLs.

The responses will be assessed at each post-baseline in-person visit except Day 0 (admission). The Day 1 assessment before IP infusion will be the Baseline observation.

### 7.1.5 Clinical Global Impression-Improvement (CGI-I)

The Clinical Global Impression – Improvement scale (CGI-I) is a 7-point scale that asks the clinician to assess how much the subject's illness has improved or worsened relative to a baseline state at the beginning of the intervention. It is rated as: 1, very much improved; 2, much improved; 3, minimally improved; 4, no change; 5, minimally worse; 6, much worse; or 7, very much worse.

CGI-I responses will be assessed at each post-baseline in-person visit.

### 7.2 Safety

### 7.2.1 Adverse Events (AE)

An AE is any untoward medical occurrence in a clinical investigation subject administered a pharmaceutical product and that does not necessarily have a causal relationship with this treatment. Data on AEs will be collected at each visit from the time the informed consent is signed until the end of the follow-up period. This includes AEs occurring during the screening phase of the study, regardless of whether or not investigational product has been administered. AEs will be coded using Medical Dictionary for Regulatory Activities (MedDRA) 20.0. Rules for partial dates are provided in Appendix 2.

#### 7.2.2 Laboratory Measures

Laboratory measures will be assessed at Screening, Day 0, +48h, and Day 11 for the IV only cohorts and at Screening and Days 0, 8, 15, 29, and 57 for the IV to oral cohort. Urine pregnancy tests and drug screens will be conducted at Screening, Day 0, +72h, and Days 11 and 34 for the IV only cohorts and at Screening and at Days 0, 8, 15, 22, 29, 36, 57, and 71. The Day 0 assessment will be the Baseline observation. Neurosteroid levels and PK data will be analyzed separately by other third-party vendors and thus will not be described in this SAP. Per protocol, the following assessments will be done.

• Chemistry: Sodium, potassium, glucose, chloride, carbon dioxide, creatinine, total protein, blood urea nitrogen, albumin, total bilirubin (with reflex fractionation to direct and indirect bilirubin if total bilirubin is elevated and outside of the normal range), alanine aminotransferase, aspartate transferase, alkaline phosphatase, thyroid stimulating hormone (with reflex to free T4 if thyroid

stimulating hormone (TSH) is outside of the normal range),  $\beta$ -HCG (Human Chorionic Gonadotropin)

- Hematology: Hematocrit, hemoglobin, red blood cell count, mean corpuscular volume, mean corpuscular hemoglobin, mean corpuscular hemoglobin concentration, platelet count, white blood cell count with differential
- Urinalysis: Leukocytes, nitrites, protein, blood, specific gravity, glucose, ketones
- Urine Drug Screen: Cannabis, oxycodone, methadone, buprenorphine, cocaine, benzodiazepines, barbiturates, alcohol (ethanol) and phencyclidine

Urine pregnancy results will only be provided in a data listing.

#### 7.2.3 Vital Signs, Height, and Weight

Vital signs will be assessed at each in-person study visit . The following measurements will be taken:.

- a. Systolic blood pressure (mmHg)
- b. Diastolic blood pressure (mmHg)
- c. Pulse rate (beats/min)
- d. Oral body temperature (degrees Celsius)
- e. Respiratory rate (breaths/min)
- f. Pulse Oximetry (%)
- g. Height (cm) (collected only at Screening)
- h. Weight (kg) (collected only at Screening and Days 0, 11, and 34 for the IV only cohorts and at Screening and Days 15, 29, 36, 57, and 71 for the IV to oral cohort)
- a. Body Mass Index (kg/m^2)

The Day 1 assessment before IP infusion will be the Baseline observation for vital signs. For weight, the Day 0 assessment will be the Baseline observation.

### 7.2.4 Columbia-Suicide Severity Rating Scale (C-SSRS)

The C-SSRS is a unique, simple, and short method of assessing both behavior and ideation that tracks all suicidal events and provides a summary of suicidality. It assesses the lethality of attempts and other features of ideation (frequency, duration, controllability, reasons for ideation, and deterrents) that are significantly predictive of completed suicide.

C-SSRS will be assessed at each in-person study visit. The Day 1 assessment before IP infusion will be the Baseline observation.

#### 7.2.5 Stanford Sleepiness Scale (SSS)

Stanford Sleepiness Scale (SSS) is a self-rated scale (1 to 8 of increasing sleepiness) measuring level of sleepiness the subject is feeling. Level 1 is "feeling active, vital, alert or wide-awake" level 7 is "no longer fighting sleep, sleep onset soon; having dream-like thoughts"; level 8 is sleeping.

The responses will be assessed at Day 1 before infusion, +8h, +32h, +56h, and +72h for the IV only cohorts and at Day 1 before infusion, +6h and at Days 2, 8, 15, 22, 29, 36, 57, and 71 for the IV to oral cohort. The Day 1 assessment before IP infusion will be the Baseline observation.

### 7.2.6 12-lead Electrocardiogram (ECG)

A 12-lead ECG will be conducted at Screening, Day 0, Day 1 before infusion, +12h, +24h, +48h, and +72h for the IV only cohorts and at Screening, +6h, and at Days 0, 2, 8, 15, 22, 29, and 36 for the IV to oral cohort. The Day 1 assessment before IP infusion will be the Baseline observation for the IV only cohorts. For the IV to oral cohort, the Day 0 assessment will be the Baseline observation. RR, PR, QRS, QTcF and QTcB will be collected. Continuous measures will be imported from an external vendor database. The data will undergo vendor specific edit checks. Reconciliations with EDC will be performed upon import of data to PRA.

### 7.2.7 Physical Examination

A complete physical examination will be performed at Screening and +72h for the IV only cohorts and at Screening and at Days 2, 15, and 29 for the IV to oral cohort.

The physical examination will include a review of the following body systems:

- Autoimmune
- Cardiovascular
- Dermatological
- Ears, Nose, Throat
- Endocrine/Metabolic
- Gastrointestinal
- Genito-urinary
- Musculoskeletal
- Respiratory
- Central Nervous System

# 8.0 **Definitions**

### 8.1 Treatment/Subject Grouping Definition

Throughout this SAP treatment refers to active or placebo. Dose refers to the dose level of the active treatment.

Label	Definition			
Study Drug	Ganaxolone			
Treatment	Ganaxolone or Placebo			
Dose Levels	Cohort 1: ganaxolone is infused at a rate of 4 mg/h (16 ml/h of ganaxolone 0.25 mg/ml solution) for 48 hours and then at a rate of 2 mg/h for the next 12 hours. The infusion is stopped at 60 hours.			
	Cohort 2: ganaxolone is infused at a rate of 8 mg/h (16 ml/h of ganaxolone 0.5 mg/ml solution) for 48 hours and then at a rate of 4 mg/h for the next 12 hours. The infusion is stopped at 60 hours.			

PRS 005 T 17 F

Cohort 3: Twelve mg bolus of ganaxolone is initially given over 2 minutes followed by ganaxolone infusion at a rate of 12 mg/h (24 ml/r of ganaxolone 0.5 mg/ml solution) for 48 hours. The rate is then reduced to 6 mg/h for the next 12 hours. The infusion is stopped at 60 hours.

Cohorts 4-5: Cohorts 4 and 5 are optional and will be utilized only if further dose exploration is warranted. Ganaxolone infusion rate will be decided based on the results of Cohorts 1-3. However, the initial bolus dose will not exceed 16 mg over 2 minutes and the maximum infusion rate will not exceed 16 mg/h.

Cohort 6: Subjects randomized to ganaxolone will receive an initial IV infusion of 20 mg/h (40 ml/h of ganaxolone 0.5 mg/ml solution) for 6 hours followed by 900 mg (4 capsules) ganaxolone capsules administered orally at dinner time for 28 days followed by a 3-day taper (3, 2, and 1 capsules per day, respectively). Subjects randomized to placebo will receive an initial IV infusion of matching placebo (at 40 ml/h) followed by 4 placebo capsules administered orally at dinner time for 28 days followed by a 3-day taper (3, 2, and 1 capsules per day, respectively). Randomization will allocate subjects to the ganaxolone arm or placebo arm in 1:1 ratio.

### 8.2 Other Definitions

#### +72h

72 hours after start of infusion (0hr) based on visit window. If a subject is discontinued from the study during the inpatient treatment phase (Day 1 through Day 4), all assessments scheduled at +72h will be collected at the time of study exit, but the assessments will be allocated to analysis visits based on visit windows detailed in Section 8.4.

### Age

The following SAS® code will be used to calculate subject age (years):

Age = floor ([intck{'month', birth date, screen date} - {day(informed consent date) < day(birth date)}] / 12), where intck is a SAS® function counting integer days.

### Baseline

Baseline is defined as the last non-missing assessment prior to the first dose of study drug. The last observation can be an unscheduled/repeated measurement. In most cases, the time point just before "start of infusion" or "0hr" will be treated as the baseline, but if this observation is missing in a given period then the screening value may be used.

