### 7.3.2 **During Infusion (Days +1 to +4)**

- Start bolus/infusion in the morning of Day +1 (0h) after baseline assessments are completed
- CTNI to conduct interviews for HAMD17 (+12h, +24h, +48h, +60h, +72h)
- Conduct interviews for CGI-I (+12h, +24h, +48h, +60h, +72h)
- EPDS (+60h)
- STAI6 (+12h, +24h, +48h, +60h, +72h)
- Collect AEs
- Collect ECG (+12h, +24h, +48h, +72h)
- Collect VS (BP, pulse, respiratory rate, pulse oximetry, temperature): (+4, +8h, +12, +18h, +24h, +32h, +40h, +48h, +56h, +60h, +72h)
- Collect SSS (+8h, +32h, +56h, +72h)
- Collect pharmacokinetic samples (+12h, +24h, +48h, +72h)
- Record concomitant medications
- Lower the infusion rate to half what was prescribed for the cohort (for example, lower the infusion rate from 4 mg/h to 2 mg/h) (+48h)
- Collect safety laboratory tests (+48h)
- Collect neurosteroid level (+48h)
- End infusion (+60h)
- Collect urine sample for urinalysis, drug screen and urine pregnancy test (+72h)
- Conduct CSSRS interview (+12h, +36h, +60h, +72h)
- Perform a physical examination (+72h)

- Stop monitoring of pulse oximetry and Q15 min health checks (+72h)
- Discharge subject (+72h)

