#### Specific timepoints for assessments on days +1, +2, +3 and +4: - Cohorts 1-5

PK samples: +12h, +24h, +48h, +72h HAMD17: before start of infusion, +12h, +24h, +48h, +60h, +72h all done by CTNI CGI-I: +12h, +24h, +48h, +60h, +72h CGI-S: before start of infusion EPDS: before start of infusion, +60h STAI6: before start of infusion, +12h, +24h, +48h, +60h, +72h ECG: +12h, +24h, +48h, +72h Vital Signs: (BP/P/pO2/RR/Temp): before start of infusion, +4, +8h, +12, +18h, +24h, +32h, +40h, +48h, +56h, +60h, +72h SSS: before start of infusion, +8h, +32h, +56h, +72h CSSRS: before start of infusion, +12h, +36h, +60, +72h Safety laboratory tests and neurosteroid level: +48h Urinalysis drug and pregnancy test: +72h Physical examination: +72h AEs and concomitant medications are collected throughout the inpatient stay.

Q15min health checks are done from the time of admission to the time of discharge. Pulse oximetry (pO2) must be monitored throughout the infusion, including during the night when the subject is sleeping. The subject should be awakened if pulse oximetry falls < 91%.

The following priority order will be in effect when more than 1 assessment is required at a particular time point: 1) HAMD17 2) CGI-I/CGI-S 3) EPDS 4) STAI6 5) SSS 6) CSSRS 7) vital signs 8) ECG 9) safety labs and neurosteroid level 10) PK sample 11) neurosteroid level 12) urinalysis drug screen and pregnancy test 13) physical examination

Day 11 and Day 34 visits have visit windows of  $\pm$  3 and  $\pm$  5 days, respectively

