Start 3-day taper		i la contra c										64	x			.

a Infusion starts at 9 am and ends 6 hours later at 3 pm and is administered at a constant rate of 40 mL/hr.

b Twelve pharmacokinetic samples are collected in Cohort 6:

On Day 1 subjects will have 6 PK samplings: at 1 hour after the end of the 6-hour infusion (i.e., at 4 pm), at 7 pm (just prior to the oral dosing), and at 1, 2, 3, and 4 hours post oral dosing (at 8, 9, 10, and 11 pm) as well at 8 am the following morning (on Day 2) prior to discharge.

A pharmacokinetic sample is also collected on Days 8, 15, 22, 29, and 36 during the study visit.

c All HAMD17 ratings, except the one done at screening, will be conducted by CTNI raters.

 $^{d}$ Q15min health checks are done from the time of start of the infusion to the time of discharge. Pulse oximetry (pO2) must be monitored from the start of the infusion throughout the inpatient period, including during the night when the subject is sleeping. The subject should be awakened if pulse oximetry falls < 91%.

e On Day +1 all efficacy assessments should be conducted first before lab draws, if possible.

f All Day +2 assessments, including PK and neurosteroid levels, are to be done before the subject is discharged from the unit.

The following priority order will be in effect when more than 1 assessment is required at a particular time point: 1) HAMD17 2) CGI-I/CGI-S 3) EPDS 4) STAI6 5) SSS 6) CSSRS 7) vital signs 8) ECG 9) safety labs and neurosteroid level 10) PK sample 11) neurosteroid level 12) urinalysis drug screen and pregnancy test 13) physical examination

All outpatient visits have  $a \pm 3$ -day visit window, except Visits 3 and 5 which have just  $a \pm 1$ -day visit window and Visits 4 and 6 which have  $a \pm 2$ -day visit window.

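### SAP 8.2 lets a missing pre-infusion value fall back to screening, past a later Day 0 value, and the ECG baseline that SAP 7.2.6 names for Cohorts 1-5 is on no schedule

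*SAP*

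**What the plan says.** The general rule is in SAP 8.2 under Baseline. It opens: "Baseline is defined as the last non-missing assessment prior to the first dose of study drug". It allows unscheduled or repeated values to qualify. It then says the time point just before infusion will serve in most cases, "but if this observation is missing in a given period then the screening value may be used". Day 0 is not mentioned.

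For ECG, SAP 7.2.6 states the schedule ("A 12-lead ECG will be conducted at Screening, Day 0, Day 1 before infusion, +12h, +24h, +48h, and +72h for the IV only cohorts") and then the baseline: "The Day 1 assessment before IP infusion will be the Baseline observation for the IV only cohorts". The next sentence treats Cohort 6 differently: "For the IV to oral cohort, the Day 0 assessment will be the Baseline observation".

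The protocol's time points for Days 1 to 4 in Cohorts 1-5, in the notes under Table 1, read "ECG: +12h, +24h, +48h, +72h".

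For HAMD17, SAP 7.1.1 takes the Day 1 pre-infusion rating as baseline. On who rates, the protocol says (Table 2 footnote c, repeated in 7.8.6.2): "All HAMD17 ratings, except the one done at screening, will be conducted by CTNI raters". Inclusion criterion 6 requires at least 26 at screening and at least 22 on the central rating on Day 0.

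**The concern.** The fallback can skip a valid, more recent measurement. That matters most where the named baseline is absent by schedule and not by accident, which is the ECG position in Cohorts 1-5.

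Safety is the study's stated purpose (SAP 12.0), and ECG is one of the four safety variables analysed as change from baseline (SAP 12.6). All four ECG criteria in SAP Table 4 use the baseline value, and the only QTcF criterion is a rise of more than 30 ms from it. If the reference visit is left open, the same woman can be flagged or not flagged according to which sentence the programmer follows, and Cohorts 1-5 may be referenced differently from Cohort 6.

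HAMD17 change is the primary efficacy endpoint. The screening score is the one rating not made centrally, and it was selected at the higher entry cut. Using it as baseline could overstate that woman's improvement.

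**Working it through.** The plan states no figure to reproduce. The check compares the texts and then does some short arithmetic.

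**1. Is a Day 1 pre-infusion ECG scheduled in Cohorts 1-5?**

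| Source | Day 0 ECG | Day 1 pre-infusion ECG | First ECG after start of infusion |
|---|---|---|---|
| Protocol 7.2 (admission) | yes | – | – |
| Protocol 7.3.1 (before infusion) | – | not listed | – |
| Protocol 7.3.2 and notes under Table 1 | – | not listed | +12h |
| SAP 6.1, its own Table 1 and notes | yes | not listed | +12h |
| SAP 7.2.6 | yes | **listed, and named as baseline** | +12h |

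The Day 1 mark for ECG in Table 1 is therefore the +12h recording. SAP 4.1 (changes from protocol) adds no ECG. The last scheduled pre-dose ECG is the one on Day 0.

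**2. What does SAP 8.2 return when the Day 1 pre-infusion value is absent?** SAP 8.4 keeps screening (Study Day below -1) and Day 0 (Study Day -1) as separate windows.

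- Variables with a Day 0 value (ECG, HAMD17, C-SSRS, vital signs): the opening sentence gives Day 0, the last sentence permits screening. They conflict.
- EPDS, STAI6 and CGI-S: collected at screening and Day 1 but not on Day 0. Both sentences give screening. They agree.

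**3. Age of the ECG reference.** The protocol counts a Day 0, so days before dosing = 1 − protocol day.

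- Day 0: 1 − 0 = 1 day.
- Screening, Day -1 to Day -14: 1 − (−1) = 2 to 1 − (−14) = 15 days.
- With the 21-day extension in Protocol 7.1, read as Day -21: 1 − (−21) = 22 days.

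**4. Effect on the QTcF flag (assumed values; the documents give none).** Take screening 400, Day 0 420 and +12h 435 ms. The change is 435 − 400 = 35 ms from screening (flagged) and 435 − 420 = 15 ms from Day 0 (not flagged).

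More generally, assume independent readings with within-woman SD s, no drift and no drug effect. The chance that one post-dose reading is flagged is P(Z > 30/(s√2)), whichever baseline is used. A simulation gave how often the two baselines disagree.

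| s (ms) | Flagged | Flag differs between the two baselines |
|---|---|---|
| 8 | 0.4% | 0.7% |
| 10 | 1.7% | 2.9% |
| 15 | 7.9% | 11.1% |

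Under these assumptions the choice changes which women are flagged, not the overall rate. Any real drift between screening and Day 0 would change the rate too.

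**5. HAMD17.** If screening exceeds Day 0 by d points, using screening adds d to that woman's improvement, raises her response cut-off (half of baseline) by d/2, and moves her arm's raw mean by d/n.

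The documents do not give d. A simulation of selection alone (screening ≥ 26 and Day 0 ≥ 22; assumed common mean 24 to 28, SD 3 to 5, correlation 0.4 to 0.8, no difference between site and central raters) gave a mean d of 0.2 to 1.8. With 10 to 30 women per cohort at 1:1, arms hold about 5 to 15. One affected woman would then move an arm's raw mean by 0.2/15 = 0.01 to 1.8/5 = 0.36 points. A rater difference would come on top and cannot be sized here.

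**The case against.** The strongest reply is that the opening sentence of SAP 8.2 is the definition, while the later one describes usual practice and says only that screening may be used. Read that way, the ECG baseline in Cohorts 1-5 is Day 0, as in Cohort 6, and a missing Day 1 HAMD17 is replaced by the Day 0 central rating. This stands as the better reading. It does not remove the defect: the permissive sentence still licenses the other choice, and SAP 7.2.6 still names an ECG that is on no schedule.

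Second, the schedules do not show that no such ECG was recorded. SAP 4.0 says the plan was also written from a CRF dated 09Aug2018, which is not available here, and 8.2 admits unscheduled pre-dose measurements. This stands, so the CRF should be checked before the time point is removed.

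Third, the fallback is right for EPDS, STAI6 and CGI-S. That also stands; the fault is its unlimited scope.

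Fourth, the consequences are modest. Flagged ECG values appear only in listings (SAP 12.6.4.2), and the analyses are mainly descriptive. The Day 1 HAMD17 is taken on the inpatient unit and has first priority among assessments, so it will seldom be missing. All of this lowers the weight of the point, especially for HAMD17, but the ECG change-from-baseline tables still need a baseline that exists.

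**Conclusion.** The SAP is wrong as written here and should be corrected. Its baseline definition contradicts itself for variables measured on Day 0, and for ECG in Cohorts 1-5 the contradiction arises by design. If the fallback were followed, the ECG reference would be about 2 to 15 days old (longer with the extension) instead of 1 day, and inconsistent with Cohort 6.

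Three stronger readings are tempting, and the documents do not support them:

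- *That all ECG changes in Cohorts 1-5 will be measured from screening.* The opening definition gives Day 0, and the fallback is optional.
- *That a screening baseline inflates HAMD17 improvement by 26 − 22 = 4 points.* Those figures are minimum entry scores, not expected scores. The true gap is unknown, and it applies only to a woman with no Day 1 rating.
- *That this favours ganaxolone.* Protocol 7.3.1 and 7.5.1 place the Day 1 rating before randomization, so treatment cannot cause it to be missing. The shift is not arm-specific, although in small arms it can fall unevenly by chance. The 3-4 point benchmark is a difference between arms, and the MMRM baseline covariate (SAP 12.5) offsets part of any shift. Raw change summaries have no such offset, and the categorical models include baseline only where applicable.

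The ECG finding rests on the schedules as written. The numerical illustrations rest on assumed values.

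**What to change.** - **SAP 8.2:** delete the screening fallback, or limit it to variables with no later pre-dose value, so that the last non-missing pre-dose value always governs. EPDS, STAI6 and CGI-S are unaffected, because that rule still returns screening for them.
- **SAP 7.2.6:** name the Day 0 ECG as baseline in all cohorts, or a later unscheduled pre-dose ECG if one was recorded. Remove the Day 1 pre-infusion time point from the Cohorts 1-5 schedule once the CRF confirms that it was not collected.
- **HAMD17 (SAP 7.1.1 or 8.2):** state that baseline is the central rating from Day 1, else the central rating from Day 0.

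The cost is a few sentences and a check of the CRF; no new data are needed. SAP 3.0 allows amendment up to unblinding. If outputs for Cohorts 1-3 already exist under SAP 10.2, confirm which ECG baseline they used.
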